ASSERT	Autism Symptoms SElf-reporT for adolescents and adults
BIS	Brief Impulsiveness Scale
BRIDGE	Brief Intensive Assessment and Integrated Formulation
BPD	Borderline Personality Disorder
BSL-23	Borderline Symptoms List -23
CAMHS	Children and Adolescent Mental Health Services
CAT	Cognitive Analytic Therapy
CI	Chief Investigator
CI	Confidence Intervals
CNORIS	Clinical Negligence and Other Risks Indemnity Scheme
CRN	Clinical Research Nurse
d-RCT	Definitive Randomised Controlled Trial
DSM-V	Diagnostic Statistic Manual-V
f-RCT	Feasibility Randomised Controlled Trial
GCP	Good Clinical Practice
GG&C	Greater Glasgow & Clyde
GP	General Practitioner
ICECAP-A	ICEpop CAPability measure for Adults
ISMS	Intensive Support and Monitoring Service
N	Number of Participants

NHS GG&C	National Health Service Greater Glasgow & Clyde
NHS R&D	National Health Service Research and Development
NRES	National Research Ethics Service
PHQ-9	Patient Health Questionnaire-9
PI	Principle Investigator
PIS	Patient Information Sheet
PPle groups	Patient and Public Involvement and engagement
RCT	Randomised Controlled Trial
SAE	Serious Adverse Event
SAP	Statistical Analysis Plan
SAU	Service as Usual
SDS	Sheehan's Disability Scale
SSC	Study Steering Group
YPAG	Young Person's Advisory Group

1 Synopsis

Short title	The BRIDGE project: A feasibility randomised controlled trial of brief, intensive assessment and integrated formulation for young people (age 14-24) early in the course of borderline personality disorder
Study Centre	University of Glasgow & NHS GG&C
Duration of Study	36 months
Objectives	To assess the feasibility of conducting a randomised controlled trial (f-RCT) of a BRIDGE, a brief intervention programme for young people (age 14-24) with early BPD (sub-threshold or threshold) in the general population of Glasgow, Scotland.
Primary Objectives	Are young people with early BPD willing to be randomised to BRIDGE (AND service as usual) or service as usual (ALONE) and can sufficient numbers of young people be recruited and retained such that a full-scale RCT is likely to be feasible?
Primary outcome	The two primary outcomes of this f-RCT are i. recruitment rates and ii. retention rates. The study will investigate the acceptability and appropriateness of our putative outcome measures for a future definitive randomised controlled trial (d-RCT).
Rationale	Young people with early BPD benefit from good clinical care and targeted intervention, however are regularly missed or mis-labelled. The feasibility trial in the general population would provide initial evidence of variable needs of young people with complex needs, who maybe missed from services as they don't "fit" a model/diagnosis. Workable multi-agency service model proposed in the trial would be a major advance in understanding care pathways regardless of trial outcome.
Methodology	We plan to conduct an f-RCT following the Medical Research Council Complex Interventions Framework.
Sample size	Our pilot work suggests that the sample size (N=60) and timescale for recruitment and randomisation, intervention delivery and for follow-up data collection is appropriately estimated. The sample of the feasibility study is adequate to estimate clinical parameters of recruitment and retention. We will

[figure not shown]
	
use the standard deviations of the putative outcome measures used in this study for the power calculations for the definitive RCT.

Screening	
The screening would include a two phased approach:
 
Screening Phase 1 : Participants (accessed through a range of clinical and non-clinical settings in Glasgow) will self-complete the brief (15-item) SCID-II PQ-BPD questionnaire. Potential participants can be either referred by a professional in a range of services in Glasgow (e.g. health, social, education) or can self-refer through advertisements in public places: everyone will complete either an online or paper screening assessment. Those meeting the cut off for the SCID-II PQ BPD (>11 out of 15) will be invited to Phase 2. SCID-II PQ-BPD has excellent psychometric properties and is used as a screening tool for BPD in outpatient youth.
 
At Screening Phase 2, all potentially eligible participants will be invited for a short (< 30 minutes) interview conducted using the Structured Clinical Interview for DSM-V Axis II Personality Disorders (SCID-II) BPD module. The eligibility criteria for the study will be those who meet subthreshold (3 or 4 out of 9 domains) or threshold (5 and above out of 9 domains) criteria on the SCID-II DSM-V, for intake to the BRIDGE study before randomisation.

Randomisation	On completion of the baseline data collection, consenting participants will be individually randomised 1:1 to BRIDGE plus service-as-usual (SAU) or SAU.
Inclusion Criteria	
 - Cut off score of 11 out of 15 on the self-reported SCID-II BPD questionnaire AND subthreshold (3 or 4 out of 9 domains) or threshold (5 and above out of 9 domains) criteria on the SCID-II DSM-V (BPD Module) - Aged between 14 and 24 years, until their 25th birthday
Exclusion Criteria	
 - Currently receiving psychological/counselling /psychotherapeutic treatment for BPD - Has received previous psychological intervention for Borderline Personality Disorder (BPD)/BPD Symptoms. - Severe or profound intellectual disability, that would preclude full engagement in talking therapy

	
 - Receiving Intensive psychiatric treatment at the time of study entry, for conditions such as acute psychosis or severe eating disorder - Non-English speaking
Intervention	
Brief, intensive assessment and integrated formulation (BRIDGE)
 
intervention development has been guided by a) the emerging evidence base for Cognitive Analytic Therapy (CAT) with young people (aged 15-25) with BPD in an early intervention service and b) in collaboration with an established Glasgow intervention programme, called Intensive Support and Monitoring Service (ISMS), used in the Glasgow youth justice system. ISMS has the explicit focus of reaching a shared formulation with the young person and the multi-agency system that supports them.
 
BRIDGE is delivered over 3-6 months and has a three-fold focus:
 
Firstly, an intensive (post-randomisation) assessment, taking up to two sessions, including BPD symptoms, copresenting difficulties, neurodevelopmental profile, life events history and psychosocial functional impact.
 
Secondly, up to 16 sessions of Cognitive Analytic Therapy (CAT)14. Thirdly, development of a shared formulation with a multi-agency group; further development of the shared formulation with the young person, using CAT principles (Reformulation, Recognition and Revision) and, where clinically applicable, their family and service-providers.
 
Services as Usual (SAU)
 
For participants randomised to SAU, a routine letter of their participation will be shared with their service provider(s), including their GP. SAU, is likely to range from social services, mental-health services, forensic services to no services in some cases. Pathways to care and service involvement will be mapped and described for each participant. Treatment fidelity to SAU will therefore not be assessed, but the nature and intensity of SAU in different contexts will be described in detail through the qualitative process evaluation.

Statistical Analysis	
Analyses carried out in the f-RCT will remain blinded. Recruitment, retention rates and the BRIDGE sessions attended will be calculated with 95% confidence intervals (CI). A simple descriptive analysis of recruitment / retention relative to eligible / approached population will be conducted. While

underpowered, between-group change in each measure after adjustment for baseline will be estimated using analysis of covariance (ANCOVA). Economic Analysis and Treatment fidelity: For the economic analysis, data will be collected on cost of delivering the intervention in addition to participant use of health, personal social services and broader educational and societal resources.

2 Trial/study summary

2.1 Participant flow diagram

2.2 Trial summary

This project is the first step in testing a new intervention programme, called BRIDGE (Brief, Intensive Assessment and Integrated Formulation), for young people early in the course of Borderline Personality Disorder (BPD). The BRIDGE Project will help us find out whether we can do a much bigger study in the future that will tell us whether BRIDGE works well. BPD is characterised by long standing difficulty in managing emotional responses, personal relationships, impulse control and self-image. Research shows that individuals with BPD may experience discrimination and resulting stigmatisation by both the public and health care professionals. Many adolescents and young people with complex needs and high suicide risk are left under-diagnosed and untreated. As a result, young people with BPD are frequently not in education or training and experience challenging relationships with friends and families. The overall aim of the study is to assess the possibility of providing a treatment programme for young people with BPD symptoms in the general population, who may or may not be accessing any mental health services. First, we need to see whether young people are comfortable with random allocation to BRIDGE (AND service as usual) or Service-as-usual (ALONE) (a bit like tossing a coin). Second, we need to find out whether enough young people want to be involved. Third, whether we can find out the information we need about them and can follow up enough young people later. The proposed study will try to find these things out, so that we can design a future, bigger, study to find out whether BRIDGE is good value for young people with BPD.

3 Introduction

3.1 Background

Borderline personality disorder (BPD) is diagnosed on the basis of a pervasive pattern of instability of interpersonal relationships, self-image, and mood as well as marked impulsivity. It is a controversial diagnosis in young people, yet those with symptoms meeting criteria for BPD are frequently under-diagnosed, untreated, are not in employment or training and estranged from their families (1).

BPD is the most common of personality disorders: in an adult population of 18 to 64-year olds, 5% meet criteria for early borderline pathology and 1.1% meet full threshold criteria (2). BPD patients have complex needs and high suicide risk, high rates of psychiatric care, social service use, psychosocial morbidity and functional impairment (3), co-morbid mental health difficulties such as depression and substance misuse (2) and reduced life expectancy (4). BPD patients are typically seen in long term outpatient care or in crisis settings, increasing the potential for iatrogenic harm and worsening the stigmatisation of BPD (5). There is now good evidence that early intervention for BPD in young people can mitigate these negative long term outcomes (6),

yet young people with BPD are often left untreated and clinically unsupported and are less likely to make transition to adult mental health services (7). The implications of this neglect is long term, evident through poor social (3) and vocational functioning (8), and potential intergenerational harm.

Young people with the persistent, complex needs characteristic of BPD – i.e. those with the poorest functioning and most complex psychiatric presentations - are often out of services by age eighteen (7). Barriers to diagnosis and treatment of BPD in young people include the myths that BPD diagnosis implies permanent disability in young people, will lead to clinical and self-experiential discrimination (9), and to widening social, health and occupational disadvantage. There is evidence from randomised controlled trials (RCTs) for the effectiveness of specialised psychotherapies for BPD in adults(10) and more recently in young people (6), but 1) effects are small and unstable at follow-up and 2) do not match the scale of the problem 3) the interventions with demonstrable effect are expensive and 4) may not be scalable at a population level.

3.2 Rationale

The worldwide social and health inequality gap is widening due to Covid-19 and will have serious implications for this most vulnerable group. Scalable approaches to mitigate the long-term psychiatric and social effects of BPD, for the benefit of the whole population, is a public health priority now, more than ever (11). This study builds on pilot work demonstrating that multi-modal recruitment methods, with excellent service user consultation, can achieve high recruitment rates of young people considered hard-to-reach. Having previously demonstrated effective recruitment from within this population, the present study seeks to assess the feasibility of conducting a randomised controlled trial of a brief intervention programme for young people aged 14-24 with sub- or full- threshold BPD, (i.e. 'early BPD') in the general population of Glasgow, Scotland.

Primarily, we want to find out if recruitment and retention rates to a brief intervention for BPD symptoms in young people, are adequate to suggest a future full-scale RCT would be possible. Furthermore, we seek to investigate the acceptability and appropriateness of accepted outcome measures for a future definitive randomised controlled trial (d-RCT) which include, at the two follow-ups: [i.] psychosocial functioning [ii.] Quality of life [iii.] emotional regulation [iv.] severity of depression [v.] impulsivity [vi.] severity of self-reported BPD symptoms. We will also attempt to capture care pathways for all participants, for the purposes of future modelling of health economics impacts, in relation to putative quality of life and functional outcomes measures. The findings will inform whether to progress to a definitive RCT and, if so, the design of a definitive trial of the BRIDGE intervention for the researchers to take forward to a large funder. It will also provide a more robust level of medium term evaluation of a BPD intervention for this population

than has previously been available, aiding practitioners and service managers in their decisions relating to BPD service provision.

Timeliness:

There is now good evidence that early intervention for BPD in young people can mitigate these negative long-term outcomes, yet young people with BPD are often left untreated and clinically unsupported and are less likely to make transition to adult mental health services. There is evidence from randomised controlled trials (RCTs) for the effectiveness of specialised psychotherapies for BPD in adults and more recently in young people, but 1) effects are small and unstable at follow-up and 2) do not match the scale of the problem 3) the interventions with demonstrable effect are expensive and 4) may not be scalable at a population level.

NICE guidelines for BPD recommend that people with BPD should not be excluded from any social and health care services but, in practice, BPD sufferers experience discrimination and disengagement from specialist services which perpetuates social and health inequalities.

The feasibility trial is a first to recruit young people with BPD symptoms, from the general population, who may otherwise be missed from specialist mental health services, especially in the current context of the pandemic, where the social and health inequalities are widening. By providing a treatment programme, which has an emerging evidence base in early intervention for BPD, the trial adds to the existing gaps in a) early identification (and description of variable needs) of BPD in the general population b) early intervention for young people through multi-agency work c) understanding care pathways regardless of trial outcome to reduce health inequalities for the vulnerable young people.

Relevance

Societal and professional attitudes to personality disorders, and the service provision that follows from these attitudes, have an important part to play in how services are delivered. One approach to furthering understanding of complex social/service delivery is 'syndemics', the term given to the co-occurrence of multiple, inter-related health problems at the individual- and population-level, developing and being sustained by harmful/unhelpful social contexts. Currently, BPD is viewed by many clinicians as intractable, entirely "trauma-related" and, where specialist services exist, treatment provision is delayed and limited to a few. Our own pilot study ('Pathways study') and work from other groups has shown that, despite their high psychiatric risk, young with BPD symptoms are less likely to be assessed/treated and often fall into the gap between child/adolescent and adult mental health services.

Our syndemics approach is our key methodology for ensuring excellent interdisciplinary working. Syndemics is embedded within the research methodology, the multi-agency intervention

approach, our international network of collaborators, and the central role of young people at all stages of study design, delivery and dissemination

4 Trial objective(s)

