4.3 Secondary outcome measures

1. How acceptable are the trial processes and interventions to the participants?
2. Can data systems be set up for assessment of both clinical and health economic outcomes in a future definitive randomised controlled trial (d-RCT)?
3. Does the trial need adapting for participants in different settings (process evaluation and qualitative interviews)?

The putative outcome measures for baseline and follow-up assessments have been selected after consulting the Delphi report from International Committee for Harmonization of Outcome Measures for Personality Disorder (http://www.netscc.ac.uk/hsdr/files/project/SDO_FR_08-1404-083_V0.1.pdf).

The f-RCT will investigate the acceptability and appropriateness of these measures for a future d-RCT which include, at screening/pre-randomisation: SCID-II PQ-BPD; SCID-II DSM-V (BPD module); KIDSCREEN10; Pathways to Care and Demographics. Post randomisation: Mini International Neuropsychiatric Interview (MINI) 7.0.2 (18yrs+) and the Mini International Neuropsychiatric Interview (MINI-KID) 7.0.2 (under 18yrs); Adverse Childhood Experiences Scale; Autism Symptoms adolescents (ASSERT); Adult ADHD Self-Report Scale (ASRS). Baseline and follow-up: Borderline symptoms list (BSL-23); Sheehan's Disability Scale (SDS); Difficulties in

Emotional Regulation Scale-SF; Patient Health Questionnaire-9; Quality of Life Questionnaire (EQ-5D); ICECAP-A; Suicidal Ideation Scale; Vocational and Educational functioning.

5 Trial design

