5.3 Measures

The putative outcome measures for baseline and follow-up assessments have been selected after consulting the Delphi report from International Committee for Harmonization of Outcome Measures for Personality Disorder (http://www.netscc.ac.uk/hsdr/files/project/SDO_FR_08-1404-083_V0_1.pdf). The f-RCT will investigate the acceptability and appropriateness of these measures for a future d-RCT which include, at screening/pre-randomisation: SCID-II PQ-BPD;

SCID-II DSM-V (BPD module); KIDSCREEN10; Pathways to Care and Demographics. Post randomisation: Mini International Neuropsychiatric Interview (MINI) 7.0.2 (18yrs+) and the Mini International Neuropsychiatric Interview (MINI-KID) 7.0.2 (under 18yrs); Adverse Childhood Experiences Scale; Autism Symptoms adolescents (ASSERT); Adult ADHD Self-Report Scale (ASRS). Baseline and follow-up: Borderline symptoms list (BSL-23); Sheehan's Disability Scale (SDS); Difficulties in Emotional Regulation Scale-SF; Patient Health Questionnaire-9; Quality of Life Questionnaire (EQ-5D); ICECAP-A; Suicidal Ideation Scale; Vocational and Educational functioning.

All the measures will be incorporated into a user-friendly questionnaire “book” and participants will have the option of completing on paper, in a telephone interview, or a mixture – a technique that has worked well in previous studies. These measures will be conducted, blind to group status, before and 12 and 24 weeks post randomization.

Analyses carried out in the f-RCT will remain blinded. Recruitment, retention rates and the BRIDGE sessions attended will be calculated with 95% confidence intervals (CI). A simple descriptive analysis of recruitment / retention relative to eligible / approached population will be conducted. While underpowered, between-group change in each measure after adjustment for baseline will be estimated using analysis of covariance (ANCOVA).

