7.2 Data Collection forms

A user-friendly booklet will be developed by the trial team incorporating relevant demographic and health economic information, as well as the following psychometrics:

Table 1. Baseline and follow-up assessments for the feasibility trial (The BRIDGE project)

Measure*	Baseline	12 wks	24 wks	What measuring?
Questionnaires				
SCID-II PQ-BPD	✓	✓	✓	BPD symptoms (self-reported)
SCID-II DSM-V (BPD module)	✓	✓	✓	BPD criteria (>3 or above out of 9 domains)
KIDSCREEN10	✓	✓	✓	Overall Functioning
Care pathways record and minimum data set	✓			Demographics, pathways to care
Questionnaires				Intensive assessment (BRIDGE)
K-SADS/PL	✓			Assessment of lifetime and present psychopathology
Adverse Childhood Experiences Scale	✓			Adverse childhood experiences
Autism Symptoms adolescents (ASSERT)	✓			Autism assessment
Adult ADHD Self-Report Scale (ASRS)	✓			ADHD symptom checklist
Putative outcome measures of change				Possible mechanisms of change
Borderline symptoms list (BSL-23)	✓	✓	✓	BPD symptom severity
Sheehan's Disability Scale (SDS)	✓	✓	✓	Functioning: work/school, social and family life
Difficulties in Emotional Regulation Scale-SF	✓	✓	✓	Domains of emotional regulation
Patient Health Questionnaire-9	✓	✓	✓	Severity of depression
Quality of life Questionnaire (EQ-5D)	✓	✓	✓	General health related quality of life

ICECAP-A	✓	✓	✓	Wellbeing assessment (Economic Evaluation)
Suicidal Ideation Scale	✓	✓	✓	Suicidal thinking and behaviours (ideation, self-harm, attempts)
Vocational and Educational functioning	✓	✓	✓	School and work (Paid and Unpaid) engagement

* The outcome measures for baseline and follow-up assessments have been selected after consulting the Delphi report from International Committee for Harmonization of Outcome Measures for Personality Disorder (http://www.netscc.ac.uk/hsdr/files/project/SDO_FR_08-1404-083_V01.pdf)

8 Randomisation

Randomisation will be controlled by the Trial Team at the University of Glasgow, who will randomise participants (1:1) to BRIDGE (+SAU) or SAU (see section 10). The trial manager will generate a randomisation list to ensure data collector blindness. The randomisation list will be stored in a password protected file within the Trial Team's private Microsoft Teams channel, and access will be restricted only to those members of the research team who will remain unblinded throughout the study. A log of access will be maintained.

9 Withdrawal & loss to follow-up

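### Section 3.2 names impulsivity among the outcome domains to be tried at both follow-ups, but no measure labelled for impulsivity is scheduled at any time point

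*Combined protocol and SAP*

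**What the plan says.** Section 3.2 (Rationale) sets out an aim beyond recruitment and retention: to examine whether candidate outcome measures are acceptable and suitable for a definitive trial. For the 12- and 24-week visits it numbers six domains, given as "i.] psychosocial functioning [ii.] Quality of life [iii.] emotional regulation [iv.] severity of depression [v.] impulsivity [vi.] severity of self-reported BPD symptoms". Impulsivity is the fifth.

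The abbreviations list defines BIS as the "Brief Impulsiveness Scale". The scale does not appear again anywhere in the document.

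The measures themselves are listed in three places.

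- **Sections 4.3 and 5.3** give the same eight measures for baseline and follow-up. In 5.3 the list starts "Baseline and follow-up: Borderline symptoms list (BSL-23); Sheehan's Disability Scale (SDS); Difficulties in" and in 4.3 it ends "Emotional Regulation Scale-SF; Patient Health Questionnaire-9; Quality of Life Questionnaire (EQ-5D); ICECAP-A; Suicidal Ideation Scale; Vocational and Educational functioning".
- **Table 1 (section 7.2)** shows what goes into the data collection booklet, with ticks by visit. The same eight measures stand in the block of putative outcome measures, whose label in the last column is "Possible mechanisms of change".

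No entry in these three places names impulsivity.

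**The concern.** A plan that names a domain as one to be tried at follow-up should schedule a measure for it. Here the domain is announced and a suitable scale is abbreviated, but neither reaches the lists from which data will be collected.

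The consequence concerns what the feasibility trial hands on. Sections 6.2, 6.3 and 12.2 say that standard deviations of the putative outcome measures will feed the power calculations for the definitive trial. Section 13.2 plans a baseline-adjusted ANCOVA for each measure. A domain without a measure receives neither, and there is no evidence on whether participants will complete or accept such a scale. Impulsivity is not peripheral in this protocol: section 3.1 includes it in the description of BPD, and section 2.2 refers to impulse control.

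**Working it through.** The plan gives no figure to reproduce, and section 6.3 states that no formal sample size calculation was made. The check compares the six domains in 3.2 with the three measure lists.

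**Step 1. Match each domain to a measure scheduled at 12 and 24 weeks.**

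| Domain in 3.2 | Follow-up measure in 4.3, 5.3 and Table 1 |
|---|---|
| Psychosocial functioning | SDS; vocational and educational functioning |
| Quality of life | EQ-5D; ICECAP-A |
| Emotional regulation | Difficulties in Emotional Regulation Scale-SF |
| Depression | PHQ-9 |
| Impulsivity | none |
| Self-reported BPD symptoms | BSL-23 |

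Table 1 also ticks KIDSCREEN10 and the SCID-II PQ-BPD at both follow-ups. These add to the first and last rows but not to impulsivity. Five of six domains are covered, so 1/6 = 17% are not.

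**Step 2. Check the rest of Table 1.** It has 16 rows. Eleven are ticked at all three visits: the eight putative outcome measures, the SCID-II PQ-BPD, the SCID-II BPD module and KIDSCREEN10. The other 16 - 11 = 5 are baseline only. Two rows might be thought to stand in for an impulsivity measure.

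- **ASRS:** baseline only, and labelled as a checklist of ADHD symptoms. It gives nothing at follow-up.
- **SCID-II BPD module:** repeated at 12 and 24 weeks. Section 3.1 makes marked impulsivity part of the BPD picture, so the module may touch the domain. Table 1, however, describes it as BPD criteria counted out of nine. No impulsivity score is specified from it.

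Whether any other listed scale contains impulsivity items cannot be established from the documents.

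**Step 3. Rule out a text-extraction fault.** A table row can be lost when a PDF is read. Sections 4.3 and 5.3 are running prose, agree with each other on the eight measures, and agree with Table 1 on those eight. No redaction is visible at these places, and the wording is current text.

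**Step 4. Locate the statement.** The six domains are enumerated only in 3.2. The general aim of judging candidate measures recurs in the synopsis (primary outcome row) and in 4.3 and 5.3, without impulsivity. Section 4.1 (objective) and section 4.2 (primary outcomes) do not mention it either.

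**The case against.** The best reply is that this is leftover text and not a gap in the design. The three operative lists agree on the outcome measures, and 4.3 and 5.3 define the set under test by naming its members. The only traces of impulsivity as an outcome are one clause in the Rationale and one unused abbreviation. That pattern fits a scale that was dropped without tidying 3.2. The reading is plausible, but the documents do not say whether the scale was dropped on purpose or omitted by mistake. Either way the text contradicts itself and needs correcting.

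Three stronger readings are tempting and are not supported.

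- **That the trial fails a stated objective.** A reader might infer this from the wording of 3.2. The sentence is an aim in the Rationale. Every objective and primary outcome in section 4 can be addressed without an impulsivity scale.
- **That impulsivity goes entirely unmeasured.** The repeated SCID-II module may capture it indirectly. The supportable statement is that no measure is labelled for it.
- **That the definitive trial would be forced to drop the domain.** Nothing in the documents limits that trial to scales tried here. It would simply choose without evidence from this study.

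One practical objection also stands. The re-engagement letter in Appendix 1 says that eighty young people have been in touch and that contact continues until December 2023, so recruitment appears to be under way. A scale added now would miss some baselines. It would also lengthen a battery that already has 11 measures at every visit, in a trial where retention is a primary outcome.

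**Conclusion.** The inconsistency is real and limited. One of the six domains that 3.2 assigns to the follow-ups has no measure labelled for it in 4.3, 5.3 or Table 1, at baseline or later. If data are collected as scheduled, the trial will yield no completion data, acceptability data, standard deviation or baseline-adjusted contrast for a dedicated impulsivity measure.

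In terms of forms, with all 60 participants retained there would be 60 x 2 = 120 follow-up assessments, and none would include such a measure. This is a ceiling, since retention is what the trial sets out to estimate, and it restates the gap without adding evidence for it.

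The conclusion assumes that the three lists are complete as printed and that the SCID-II module is used as Table 1 describes it. Recruitment, retention and the section 4 objectives are untouched. The point deserves correction because the trial is meant to inform the choice of outcomes for the definitive trial, and the correction is cheap.

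**What to change.** Decide whether impulsivity is still a candidate outcome for the definitive trial, and make the sections agree.

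1. **If it is,** add the BIS to sections 4.3 and 5.3 and to Table 1 at baseline, 12 and 24 weeks. The cost is an amendment and one more brief scale in the booklet. Anyone already enrolled would lack a baseline score and could contribute only follow-up acceptability and standard deviation data, so the baseline-adjusted contrast would rest on later entrants. The SAP should say so.
2. **If it is not,** delete impulsivity from the domains in 3.2 and BIS from the abbreviations, and state that the trial does not inform this domain for the definitive trial. The cost is a short text change and a narrower aim. This option is open at any stage of recruitment.
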